### C.7. Timeline

Table 7. Timeline of planned research activities										
Research Task	Month of Study									
	6	12	18	24	30	36	42	48	54	60
Convene weekly research meetings (key personnel)										●
CAB meetings	●	●	●	●	●	●	●	●	●	●
In-person training of home visitors and refresher courses	●	●		●		●				
Delivering COPE as part of HVP services									●	
Recruitment /enrollment /baseline assessment										
33% sample			●							
66% sample				●						
100% sample					●					
Assessments (based on rolling enrollment)										
6-month assessment						●				
18-month assessment								●		
Data entry and data cleaning										
Interim analyses and preliminary reports and publications									●	
Manuscript preparation and research dissemination										●
Clinical and community dissemination										●

**C.8. Deliverables.** The most appropriate scientific outlets will be journals dedicated to obesity (International Journal of Obesity, Pediatric Obesity) and general nutrition and public health (Pediatrics, American Journal of Public Health, American Journal of Clinical Nutrition). We will also target specialized (Obesity Society, International Network for Social Network Analysis) and general conferences. Study findings will be disseminated to our HVP partners, Community Advisory Board and key stakeholders, and utilized to refine our existing curriculum and protocol for future dissemination.

## PROTECTION OF HUMAN SUBJECTS

### A. Participants

This comparative effectiveness research involves the enrollment of 300 mothers/infants for a final effective sample of 200 mothers and their infants (age 6mo at enrollment).

**Inclusion of women.** Women are represented by mothers and female infants, which will be about half of the infant sample. Based on our projected effective sample of 200 mothers and their 200 infants (N=400), we anticipate that 75% of our sample will be women (100 children + 200 mothers = 300).

**Inclusion of racially and ethnically diverse families.** The families enrolled in the Home Visiting Program (HVP) from which the sample is drawn is culturally, racially and ethnically diverse, reflecting the population of low-income families enrolled in home visiting services in the Antelope Valley, CA area. Based on our HVP partner (Healthy Families America site in Southern California: Antelope Valley Partners for Health and Children's Bureau) clients' demographics and on our pilot work, we anticipate the following ethnic and racial distribution: 70% Hispanic/ Latino, 13% African American, 8% White, 5% American Indian/Alaskan, and 4% mixed/other race.

It is important to note that Health Families America (HFA) home visitors are matched to families based on language and cultural background. Home visitors are rigorously trained to understand, acknowledge, and respect families' cultural differences. Home visitors are selected because of their personal characteristics (i.e. non-judgmental, compassionate, ability to establish a trusting relationship, etc.), their experience working with culturally diverse communities, and their skills to do the job.

**Inclusion of children.** Infancy and early childhood are important developmental periods given that nearly one-third of American children two years and older are already overweight or obese and these rates are even higher among low-income children of color. Once obesity is established, it is difficult to reverse, and obesity in childhood and adolescence are independent risk factors for adult obesity. Children develop eating and activity habits in the context of their family, and parents influence the child's health trajectories through their own behaviors (e.g., modeling) and through the shared family environment. This proposal addresses the impetus to develop interventions targeting at-risk infants before obesity is established, to avoid the significant public health implications associated with obesity by reducing lifelong health struggles for at-risk individuals and reducing financial burdens for the society as a whole. The services and obesity module being evaluated in this proposed research involve the provision of home visiting services to infants/children and their mothers. Therefore, a number of the outcomes that will be measured as part of the proposed research will involve children. Specifically, children will be represented by the 200 infants that will be the offspring of the mothers, as well as mothers who are 18 years of age or younger. A significant proportion of mothers enrolled in home visiting services (50%) are ≤18 years of age. Based on our pilot data, we expect the total number of participants ≤18 years of age at enrollment will be: 200 infants + 100 mothers = 300.

The research team is well trained and experienced in conducting research in children. [name] (MPI) is a Clinical Psychologist with expertise in pediatric and child psychology, and she has been a member of the children's Institutional Review Board (IRB) for several years at the Women and Children's Hospital in Buffalo, NY. She will ensure the quality of the treatment implementation. The involvement of minors as participants in this research is in compliance with all subparts of 45 CFR Part 46 as well as with Federal laws and regulations.

**Sources of materials.** Data will be used specifically for research purposes and held in strict confidence. Data from human subjects include:

- Clinical evaluation and medical history via questionnaire/interview;
- Demographic information, via questionnaire (mothers)
- Anthropometry: body weight, waist circumference, height (mothers/infants)
- Blood pressure (mothers) and blood samples (mothers/infants);
- Variables derived from dietary intake, via recall interviews (mothers as respondents for themselves and for their infants);
- Physical activity via interview/recall (infants) and accelerometers (mothers);
- Social networks and support via questionnaires (mothers);
- Maternal feeding style & practices via questionnaire (mothers);
- Maternal food insecurity via questionnaire (mothers);

**Records.** Mothers' pre-pregnancy weight and infants' birth weight will be obtained from our HVP partner. All other data used for this study will be collected during the implementation of the study protocol.

### B. Potential Risks/Adverse Events and Procedures Used to Minimize the Risks

For purposes of monitoring and reporting adverse events, the following definitions will be used:

**Adverse event (AE):** any untoward medical occurrence that may present itself during treatment or administration of an intervention, and which may or may not have a causal relationship with the treatment. Adverse events could arise from the study (e.g., breach of confidentiality) or could arise because of the population under study (e.g., a mother reports extensive use of drugs).

**Serious adverse event (SAE):** Any medical occurrence that results in death; is life-threatening; requires inpatient hospitalization or prolongation of existing hospitalizations; creates persistent or significant disability/incapacity, or a congenital anomaly/birth defect. Such an event could include suicidal ideation or attempted drug overdose or withdrawal, etc.

**Adverse events monitoring.** Each participant (mother and infant) will be evaluated for any adverse events. All events will be graded by their attribution (unrelated to protocol; or possibly, probably, or definitely related to protocol). Any event reported to the Principal Investigators or to designated research associates by the subjects or Antelope Valley Partners for Health nursing and medical staff, which also meets the event criteria, will be carefully documented in a report submitted to the IRBs. The report will include a description of the event; when and how it was reported; any official charts, records, or documentation to corroborate the event or the reporting of the event; and an action plan to prevent future occurrences. All adverse events will be graded as mild, moderate, or severe. Any severe and/or unanticipated adverse event will be immediately reported to the IRBs (within 48 hours of occurrence or recognition) and NIH. All adverse events will be summarized annually and submitted to the IRBs and NIH. Any action resulting in a temporary or permanent suspension of this study (e.g., IRB actions) will be reported to the NIH.

**Physical risks.** There are minimal physical risks added from participating in this study. All lifestyle dietary and physical activities suggested are in line with national guidelines. Recommended physical activities are low impact and unlikely to create discomfort for participants.

**Psychological risks.** Though none of the questionnaires contain items that are particularly sensitive, personal, or potentially upsetting, it is possible that a participant may become upset thinking about some of the questions or topics in this study. Trained assessors will be conducting the assessment sessions to address any potential incident. All participants will be informed that they are free to refuse to answer any particular questions or questionnaires. They will also be informed that they can withdraw from the study at any time without penalty. Staff will immediately report any AEs connected to the implementation of the intervention to Drs. [name] and [name] who will keep a log of AEs and SAEs. Drs. [name] and [name] will file a written report within 24 hours of being notified to the IRB, whether the event relates to the project or not. As part of this process, members of the IRB committee review the event and determine whether the event is directly related to project procedures so that it can be determined whether procedures need to be modified to avoid a similar AE in the future. Whether the event is related to the project, we will keep a log to provide information about all AEs in annual progress reports to the IRB and NIH. Drs. [name] and [name] will monitor outcomes for AEs, and outcome information will be entered into a log for inclusion in reports to the IRB and NIH.

**Social risks.** There are no social risks for participating in this study.

**Legal/other risks.** None.

**Postpartum depression.** The Edinburgh Postnatal Depression Scale (EPDS) is used to assess *postpartum depression* at enrollment into home visiting services. Maternal depression will be assessed again prior to study enrollment. Mothers who show signs of severe postpartum depression will be closely monitored and provided additional referrals and resources as needed. The Safety Officer, [name], is a physician at the Antelope Valley Clinic. [name] oversees the physical and psychosocial safety and well-being of families enrolled in home visiting services. The decision to include/exclude mothers with postpartum depression will be taken on a case-by-case basis with the counsel of one of the PI ([name], Psychologist), Antelope Valley Partners for Health directors, the Safety Officer ([name], DO) and our CAB (which includes mental health professionals and [name], MD). We believe that some mothers may benefit from engaging in positive and reinforcing activities such as cooking and lifestyle activities. Physical activity has been shown to improve moods and alleviate symptoms of depression.

**Trauma and domestic violence.** If we suspect that mothers are victims of intimate partner violence, either through completion of the questionnaires or through mother report or staff observation, we will implement the following procedures: (1) we will make mothers aware of resources available to them in their communities, such as shelters; (2) we will work with mothers to develop a safety plan for addressing violence and seeking shelter; (3) we will ascertain risk to the child. If we suspect that the child has been abused or witnessed domestic violence, we will make a report to child protective services. We will work closely with the home visitor and our HVP partner to coordinate efforts in the best interests of the mother and child. Mothers who are victims of domestic violence will not be dropped from the study.

**Suicidal behavior.** As we will be measuring depression in mothers, we will potentially identify participants who are suicidal. We follow the Substance Abuse and Mental Health Services Administration SAFE-T: Suicide Assessment Five-Step Evaluation and Triage approach to determining risk and clinical response. The five steps are Identify Risk Factors, Identify Protective Factors, Conduct Suicide Inquiry, Determine Risk Level/Intervention, and Document (which includes intervention and follow-up). As per Practice Guidelines, we will estimate suicide risk as Low, Moderate, or High. All potentially suicidal mothers will be provided an emergency plan with numbers to call, including local hospital emergency rooms, suicide hotlines, and home visitor contacts. Each plan will be individually tailored to the needs and resources of the mother. Family members will be incorporated into the plan. We will be available to home visitors and our HVP partner to work with them as to how to proceed if their clients present with suicidal behavior. Home visitors also have ready access to supervisors in their agencies to help them respond to mental health needs, and some of the agencies run separate mental health programs, thereby providing additional resources for home visitors in conjunction with project staff. Mothers who experience psychiatric emergencies such as suicidal behavior will not be dropped from the study.

**Alternative treatments.** Parents who do not want to receive the nutrition and physical activity module (i.e., COPE), will receive the standard home visitation program curricula.

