complete rigorous training to learn the HVP curriculum and meet the requirements of Healthy Families America (the HVP model we are partnering with). They receive weekly supervision to review progress and address issues. (3) Home visitors delivering COPE receive a 2-day initial training and annual refresher courses from [name] and the onsite Health Families America dietitian and nutritionist, with scripted manuals and materials. [name] further reviews 25% of the sessions to monitor fidelity. (4) Weekly supervisions (home visitors) and bi-annual focus groups (families, home visitors, and Community Advisory Board) are conducted to review progress, dosage and timing of delivery, and provide the opportunity to resolve problems or issues encountered. (5) Intervention components are delivered in the home or at specified community-run settings (e.g., community garden), and meetings and supervisions with home visitors implementing different arms are held on separate days (at Antelope Valley Partners for Health) to minimize the risks of contamination. COPE supervision is embedded in the weekly supervision home visitors already receive to monitor their services. **Potential burden or weakening of HVP curriculum.** Potential concerns related to adding material to the existing HVP curriculum include (1) diluting or weakening HVPs' outcomes in other areas (e.g., parenting skills, maternal depression), and (2) increasing the burden on HVP staff and families. Our formative evaluation and pilot work indicate that these concerns are unfounded. COPE was designed collaboratively with our HVP partners (who are experienced in integrating new enhancement modules into the HVP curriculum) so that it would complement other program goals. For instance, home visitors report that COPE cooking and tasting activities are used to strengthen mother-child bonding and parenting skills (a standard HVP benchmark area). HVP directors also found no differences between HVP+COPE and HVP only families on HVPs' benchmark areas set by the Health Resources and Services Administration (i.e., maternal and newborn health; child abuse and neglect and emergency department visits; crime or domestic violence; family economic security; and coordination and referrals for other community resources and support). Concerns that COPE may overly burden families and lead to greater attrition was also not supported, as the dropout rate was considerably *lower* among mothers in the HVP+COPE group than among mothers in the HVP only group in our pilot study. These findings suggest that the addition of COPE does not weaken other HVPs' targeted outcomes, or overly burden families and home visitors. We will continue to monitor these outcomes throughout the implementation.

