**C.5. Measurements.** HVP *Assessment Workers* (registered nurses who can draw blood) who enroll families into standard HVP services, have been trained to screen and recruit eligible families for the proposed project. They will administer the assessments (English or Spanish; **Table 6**) in the families’ homes or at the HVP clinic (as needed) at baseline/enrollment, and after 6mo and 12mo of services. *Home visitors* will be trained to gather interim (objective) weight measurements for the purpose of generating more frequent data points, triangulated with the assessment workers’ measurements.

**Medical and family history.** A thorough family history and physical examination will be conducted at baseline. We will collect demographic data, including socioeconomic status (education, income, eligibility for SNAP).

**Infant growth & waist trajectories.** Weight will be measured on a digital scale (Tanita) accurate to the nearest 5g. Length will be measured to the nearest 0.1 cm using an infanto-meter using the standardized WHO approach,

Table 6. Assessment time points (month of intervention) and key measures							
	Baseline	3	6	9	12	15	18
COVARIATES							
Demographics, household composition, medical history, post-partum depression, activity readiness	X						
MOTHERS							
Weight/height, waist circumference	X	X	X	X	X	X	X
Blood and vitals	X						X
24h diet & activity recall	X		X				X
Feeding and food insecurity	X		X				X
Social support and networks	X		X				X
Home environment	X		X				X
INFANTS							
Weight/length, waist circumference	X	X	X	X	X	X	X
Blood (finger prick)	X						X
24h diet & activity recall (from mother)	X		X				X

including use of staff training modules. Weight and length will be used to calculate weight-for-length and weight-for-age z-scores (WHO Standards), as recommended by the CDC for children <24 mos. Infant growth rates will be examined as the change in WLZ from baseline to follow up (12mo) Waist circumference will be measured at the umbilicus (nearest 1-mm) using a non-stretch measuring tape.

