## C.6. Analytic Plan.

**General strategy.** Three waves of data will be collected (baseline/enrollment, 6 and 12- months of intervention). Analyses will be carried out according to the intention-to-treat rule consistent with standard practice in most clinical trials. We will conduct standard statistical diagnosis and descriptive statistics of demographic and background variables, and examine frequencies for reasonableness, sparseness (categorical data) and non-normality (continuous variables) of the data. Missing data will be addressed using multiple imputation and/or full information maximum likelihood estimation. Psychometric properties of the study scales will be investigated to ascertain appropriate validity and reliability. Preliminary analyses will test group equivalence on baseline characteristics. Categorical methods of analysis (e.g., cross tabulations, chi-square) will be used for discrete data while *t*-tests will be used for continuous data to test the comparability of the prevention arms. Factors found to be different at baseline will be adjusted for in subsequent analyses. The following **covariates** will be entered in all analyses: home visitor, home visitor experience (years), number of visits, household composition, race/ethnicity, acculturation, mother's age, medical history/gestational diabetes, post-partum depression.

**Social network analysis (SNA).** Network data will be analyzed using SNA packages in R (e.g., SNA, igraph) to produce visualizations and statistics that summarize the characteristics of each mothers' network. We will compute the following network statistics: the proportion of network members that provide specific types of health relevant support, and that engage in specific health behaviors; and the density of supportive relationships within each network (i.e., the number of supportive relationships among network members that are reported, as a proportion of the total number of possible supportive relationships where all network members provide support). These statistics will be computed for each assessment period (as well as change statistics across periods), and included in the analyses, as described below.

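### No depression measure is scheduled after study entry, although the plan relies on one to monitor maternal depression and to identify suicidal mothers

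*Combined protocol and SAP*

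**What the plan says.** Depression is measured up to study entry:

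- Protection of Human Subjects, section B (Postpartum depression): the EPDS is given at entry to home visiting, and then "Maternal depression will be assessed again prior to study enrollment". No instrument is named for the second assessment, and no later one is mentioned.
- Section C.5, Table 6: the covariate row "Demographics, household composition, medical history, post-partum depression, activity readiness" has a mark at Baseline and nowhere else.
- Section C.6: the covariates for all analyses include "medical history/gestational diabetes, post-partum depression". Depression is not listed as an outcome.

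Three statements look beyond entry:

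- Section C.2 (potential burden or weakening of the HVP curriculum) raises the possibility that COPE dilutes HVP "outcomes in other areas (e.g., parenting skills, maternal depression"). The paragraph ends: "We will continue to monitor these outcomes throughout the implementation".
- Protection of Human Subjects, section B (Suicidal behavior): "As we will be measuring depression in mothers, we will potentially identify participants who are suicidal". The SAFE-T triage procedure follows.
- Same section (Postpartum depression): "Mothers who show signs of severe postpartum depression will be closely monitored and provided additional referrals and resources as needed". No instrument, interval or duration is given.

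**The concern.** The plan raises maternal depression both as a possible unintended effect of adding COPE and as the means of finding mothers at risk of suicide. Either use during the intervention needs a value taken after baseline, and the written schedule contains none.

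Two things are at stake. The first is safety ascertainment: new or worsening depression after entry has no scheduled study measure in either arm, and the triage procedure for suicidality has no scheduled trigger while COPE is being delivered. The second is the dilution question in section C.2: with only a baseline value, the study's own data cannot show whether depression moved differently in the two arms.

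The population adds weight. Mothers with postpartum depression may be included case by case, mothers with suicidal behavior stay in the study, half of the mothers are expected to be 18 or younger, and many are described as socially isolated. Suicidal ideation is given as an example of a serious adverse event.

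**Working it through.** No sample size, power or event figure bears on this point, so the check is a count and a comparison of sections.

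**Count of scheduled depression assessments**

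- Up to study entry: 2 (entry to home visiting; before study enrollment). The baseline mark in Table 6 is taken to be the second of these.
- After baseline in Table 6: 0 of 6 columns (3, 6, 9, 12, 15 and 18 months).
- At the follow-up waves in section C.6: 0 of 2 (6 and 12 months). Table 6 places the later full battery at 18 months rather than 12. That conflict is separate, and the count is zero on either reading.

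**Search for another instrument.** The maternal measures in section C.5 cover anthropometry, blood and vitals, diet and activity, social networks and support, and food insecurity. The PROMIS items concern emotional and instrumental support and social isolation, not depression. No suicidality scale appears.

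**Statements against schedule**

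| Statement | What it needs during the intervention | What is scheduled |
|---|---|---|
| C.2: HVP outcomes, with depression as an example, monitored throughout | A repeated value in both arms, or a named external source | No study measure; no source named |
| Suicidal behavior: mothers found because depression is measured | A depression measure after entry | None after entry |
| Postpartum depression: close monitoring of severe cases | Some follow-up of mothers already flagged | No instrument or interval; can be met clinically |

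The third row is not a contradiction, because clinical follow-up of a flagged mother does not require a repeated scale. The first two rows are unsupported by the schedule as written.

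**What remains during the intervention.** Weekly home visits, adverse event evaluation of every mother, and the Safety Officer all operate in both arms. The adverse event text works from events reported by participants or by nursing and medical staff, and gives no depression questions or fixed times. Home visitors deliver the assigned curriculum and so know the arm. Section C.4 adds communal activities promoted to the COPE arm only, so opportunities for disclosure may differ by arm. Case reports gathered in this way are not a like-for-like comparison. By contrast, section C.1 has assessment workers who are blind to assignment carry out the follow-up assessments, but the schedule gives them no depression measure.

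**The case against.** The strongest reply is that section C.2 is not describing a study instrument at all. Just before the monitoring sentence, it reports that HVP directors compared the two groups on federal benchmark areas, one of which is maternal and newborn health. On that reading, continued monitoring means the partner's own by-arm comparison, and the partner may well repeat a depression screen as part of its services. This stands to the extent that such data cannot be ruled out. It does not settle the matter: the listed benchmark areas do not name depression, and no section says that the partner repeats a depression score after entry or that the study will use it.

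The second reply is that safety oversight is substantial: weekly visits by staff trained in mental health referral, weekly supervision, adverse event evaluation, SAFE-T with an active suicide inquiry, a Safety Officer, monthly reviews by the principal investigators and a DSMB twice a year. This stands in full as a description of detection routes.

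It also rules out stronger readings that a reader might infer. One is that depression and suicidality are promised to be monitored throughout as study risks and that this cannot be done. The safety section makes no such promise: it limits close monitoring to mothers with severe signs and says only that suicidal mothers may be identified. The commitment to monitor throughout comes from section C.2 and concerns HVP outcomes. Another is that only spontaneous disclosure is left, or that no mother is ever screened again. The routes above contradict the first, and Table 6 lists study measures, not everything the HVP does.

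**Conclusion.** The point holds in a limited form. The study schedules no depression or suicidality measure after entry: 0 of 6 later columns in Table 6 and 0 of 2 follow-up waves. Two statements, in section C.2 and in the Suicidal behavior paragraph, therefore have no stated post-entry measure behind them. Detection during the intervention rests on unstructured observation and reports, largely from unblinded home visitors, and the planned data contain no arm-comparable post-baseline depression value.

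This rests on reading Table 6 and section C.5 as the full set of study measures. It would be answered if the sponsor identified repeat depression data held by the HVP partner. The number of mothers affected cannot be estimated, because the documents give no rate of new depression after entry.

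This is a gap in safety ascertainment and in the answer to the plan's own dilution question. Depression enters the efficacy models only as a covariate, so the primary efficacy analysis is not affected. It is worth correcting because the correction is inexpensive.

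**What to change.** Reconcile section C.2, Table 6, and the Postpartum depression and Suicidal behavior paragraphs so that they agree on what is measured, when and by whom. One of three routes would do:

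1. Name the depression scale used at baseline and add it to the mothers' block of Table 6 at the existing full follow-up assessments, in both arms, administered by the blinded assessment workers. Report the post-baseline values by arm to the DSMB and in the results. The conflict over whether the later full assessment falls at 12 or 18 months must be settled at the same time.
2. If the HVP partner already repeats a depression measure, name it, state its timing in both arms, and say how the study will obtain and report it by arm.
3. If neither is intended, withdraw or limit the statement in C.2 as it applies to depression, and restate the Suicidal behavior paragraph so that it claims identification through measured depression only up to study entry.

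How positive results are handled clinically is for the sponsor to settle.

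The cost of the first route is a short questionnaire (the EPDS has 10 items, according to the title of its cited reference) at visits already scheduled, and staff time for some additional alerts. The second needs a data-sharing arrangement; the third needs only a text change but leaves the dilution question unanswered for depression.
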